A written informed consent will be obtained from each patient included after explanation of the risks and benefits of participating in this study. No change in the trial design will be made after approval of the Ethics Committee.

Intervention

Age, sex, smoking habits should be recorded. At Baseline examination taken by (RA) the following periodontal index will be recorded at 6 sites per tooth.

- **P.P.D**: measured from the gingival margin to the bottom of the pocket.
- G.I. recorded as presence or absence of bleeding after gently run on the surface of the

marginal gingiva.

- **PI**: recorded as presence or absence of plaque. A probe will gently run on the surface of the teeth.
- **REC:** measured from the cement-enamel junction to the gingival margin.
- CAL: measured clinically from the base of the pocket to the cement-enamel junction

A PCP-UNC 15 periodontal probe is used on six sites per tooth (mesio-buccal, buccal, distobuccal, mesio-lingual, lingual and disto-lingual) with a gentle probing force by the same examiner. Measurements are rounded to the nearest millimetre.

Examiner calibration:

The examiner should be calibrated measuring PPD and PAL in one quadrant with at least 6 teeth on 10 patients. Measurements should be repeated after one hour and variability should be assessed

After baseline recording (RA), a professional oral hygiene (full mouth erythritol powder air polishing therapy – FM-EPAPT) will be done by VB.

After ultrasonic debridment the randomization envelope will be open by VB.

Group A: sonic toothbrush (Philips Sonicare Flexcare Platinum Toothbrush®) will be given

Group B: Manual brushing (Technique Pro - GUM® Sunstar Italiana SRL) will be given.

For each group specific instruction of oral hygiene will be done.

For all patient are recommended: toothbrush Hydral Gum (GUM® Sunstar Italiana SRL) and interdental floss (GUM® Sunstar Italiana SRL)

Each patient is recalled at 2 and 4 weeks to reinforce oral hygiene instructions (VB) and do collect GI and PI (RA).

Furthermore, all patients are recalled at 6 weeks 6 and 12 months for update of periodontal folder (RA); at 6 and 12 months professional hygiene will be done by VB.

At the end of the therapy reinforcement of oral hygiene instruction are given by VB.

Primary Outocome:

Change in P.I.. change in 10% of the site in test group.

Secondary Outcomes:

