**Change in G.I.**: change in presence or absence of bleeding after gently run on the surface of the marginal gingiva.

Change in R.E.C.: change in gingival reduction.

Change in C.A.L. change in clinical attachment level.

Sample size determination

We assumed that count of sites with plaque within patient can be described by a Poisson distribution. Assuming a fixed number of sites per patient (N=48) we can model the data using a Poisson-rate model and therefore estimate the number of patients needed to achieve approximately 10% reduction (as a difference between rates) in the P.I. rate between the two treatments, corresponding to approximately 30% proportional reduction. For simplicity we considered only the effect at the latest time point. The we simulated Poisson counts for a set of candidate sample size assuming a drop from a 25% rate (12/48) to 17% (8/48) and modelled the data using a Poisson regression (GLM with Poisson family). We performed the simulation 500 times and computed the proportion of time the coefficient for the two group comparison had a p-value lower than 5%. A sample size of 16 for each groups allowed a power of at least 90%.

Statistical Analysis Plan

Data will be aggregated within patient to compute the number of site with plaque over the total number of probed sites (i.e. P.I.). Counts will be modelled using a Poisson rate model (GLMM with Poisson family) and setting the total number of site per patient as offset. A significance level of 5% will be used and all the analysis will be performed using the software R.

Randomization

Patients will be randomized to either treatment using a computer generated sequence based on a blocked randomization procedure. The software used will be R.

Summary of the procedures:

Baseline:

- clinical measurements: PPD, PI, GI, REC, CAL.
- FM-EPAPT
- randomization
- education and motivation
- 2/4 weeks:
- education and motivation
- checking compliance
- GI and PI

6 weeks:

- education and motivation
- checking compliance
- clinical measurements: PPD, PI, GI, REC, CAL.

6/12 months:

- clinical measurements: PPD, PI, GI, REC, CAL.
- FM-EPAPT
- checking compliance
- education and motivation

Drop-outs:

All drop-outs should be reported and the reason for dropping out should be investigated and reported per study group.

Publication plan:

2, 6 and 12 months results

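### Minor, cheap improvement: name the last-visit contrast that was sized as the primary test, and adjust it for the baseline plaque index already recorded before allocation

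*Protocol*

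**What the plan says.** Four parts of the protocol bear on this.

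- **Primary outcome.** The outcome is a change in PI, described only as "change in 10% of the site in test group". No reference visit, time point or between-arm contrast is given.
- **Sample size determination.** The sizing works from one visit: "For simplicity we considered only the effect at the latest time point". It starts with "Assuming a fixed number of sites per patient (N=48"), takes 12/48 against 8/48, and then "modelled the data using a Poisson regression (GLM with Poisson family"). The result is "A sample size of 16 for each groups allowed a power of at least 90" per cent. Baseline does not enter.
- **Statistical Analysis Plan.** The model is given in one sentence: "Counts will be modelled using a Poisson rate model (GLMM with Poisson family) and setting the total number of site per patient as offset". No fixed or random effect is named: not group, visit or baseline.
- **Intervention.** PI is recorded at the baseline examination, before the professional cleaning. Allocation is revealed only later: "After ultrasonic debridment the randomization envelope will be open". PI is collected again at 2 and 4 weeks, and "all patients are recalled at 6 weeks 6 and 12 months for update of periodontal folder". That makes five post-baseline visits, the last at 12 months.

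**The concern.** The outcome is worded as a change, the power belongs to a last-visit count, and the model says nothing about how baseline PI enters. A reader therefore cannot tell which analysis the 90% describes. The words allow a last-visit contrast, a last-visit contrast adjusted for baseline, or a group-by-time test with baseline as a visit, and these differ in power.

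Validity is not at stake: with randomised arms, an unadjusted last-visit contrast is unbiased. What is at stake is some precision in a trial of 32 patients, and a clear link between the outcome, the power statement and the test. Baseline PI is measured before allocation is known, so it is a legitimate covariate. Patients with PI below 25% are excluded, so its logarithm is always defined.

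**Working it through.** **1. The protocol's own figure.** Inputs from Sample size determination: 48 sites, means 12 and 8, 16 per arm, 5% level (two-sided assumed, since sidedness is not stated).

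- Effect: ln(12/8) = 0.4055.
- Variance: 1/(16×12) + 1/(16×8) = 0.00521 + 0.00781 = 0.01302, so SE = 0.1141.
- Power: Φ(0.4055/0.1141 − 1.96) = 94.4%; 200,000 simulated trials give 94.9%. Taking 17% literally (8.16 sites) gives 92.5%.

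The stated power is reproduced.

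**2. Cost of adjustment on those inputs.** The setting is five post-baseline visits, a patient random intercept, the contrast at 12 months, 48 sites and no between-patient variation.

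| Analysis | Unadjusted | Adjusted for log baseline PI |
|---|---|---|
| Multi-visit Poisson GLMM | 94.7% | 94.6% |
| Last visit alone | 94.0% | 93.4% |

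With 4,000 trials per setting, the simulation error of one such estimate is √(0.947×0.053/4000) = 0.35 points, so the 0.1-point difference is negligible.

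**3. Gain if baseline predicts follow-up.** The protocol gives no between-patient variation, mean baseline PI or correlation. Assumed: log SD 0.3 to 0.5, mean baseline 40 to 55%, 48 or 120 sites.

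| Assumed baseline-to-12-month correlation | Adjusted minus unadjusted GLMM power (points) |
|---|---|
| 0 | −0.9 to +0.2 |
| 0.3 | +0.2 to +2.5 |
| 0.5 | +1.7 to +7.0 |
| 0.65 | +3.8 to +13.0 |
| 0.8 | +6.1 to +22.8 |

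Gains above 10 points arise only with SD 0.5 and a correlation of 0.65 or more, which nothing in the protocol supports. In single-visit linear models on log PI, adjustment changes power by −1.8 to −0.9 points at correlation 0 and by +0.9 to +5.4 at 0.5.

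**4. What adjustment does not do.** Absolute GLMM power at 48 sites, unadjusted then adjusted:

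| Log SD | Correlation 0 | 0.5 | 0.8 |
|---|---|---|---|
| 0.3 | 75%, 75% | 77%, 78–80% | 76–78%, 85% |
| 0.5 | 51%, 51% | 51–54%, 57–58% | 55–60%, 74% |

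If patients differ this much, adjustment does not restore 90%.

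**5. False-positive rate at 48 sites.** Adjusted 4.1 to 6.4%, unadjusted 4.3 to 6.5%. If post-baseline visits correlate only 0.7, these become 6.9 to 11.0% and 6.9 to 9.7%. That is a limit of a patient-intercept-only model, with or without baseline.

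**6. Conditional illustration: change tested as group-by-time on the log-rate scale.** With assumed mean baseline PI b, the variance gains 2/(16×48×b). At b = 25% it is 0.01302 + 0.01042 = 0.02344, and power is Φ(0.4055/0.1531 − 1.96) = 75.4%.

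| Assumed mean baseline PI | Poisson counts (formula) | Binomial counts at both visits (simulated) |
|---|---|---|
| 25% | 75.4% | 78.5% |
| 40% | 82.7% | 86.9% |
| 55% | 86.1% | 90.6% |
| 70% | 88.0% | 92.6% |

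All rows assume 48 sites, 16 per arm and no between-patient variation. At 120 sites (5 teeth × 4 quadrants × 6 sites) power is about 99% or more.

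**The case against.** The strongest defence is that nothing here is wrong. The sizing is openly a simplification. The 10% in the outcome matches the 10% between-arm difference in Sample size determination, so a between-arm contrast is a plausible meaning of the outcome, and that is what was powered. Model terms are commonly left to a SAP, which may exist. The benefit of adjusting rests on a variance and a correlation that the protocol does not supply. All of this stands, and it limits the point to an improvement.

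Two stronger readings are tempting and not supported.

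- A reader might infer that the trial has only 75 to 88% power for its primary outcome. That range needs a group-by-time test that no section specifies, an assumed mean baseline PI (25% is only the entry floor, so a mean of 25% puts every patient exactly on it), Poisson baseline counts, 48 sites and no between-patient variation. With binomial counts it reaches about 90% or more at the upper baselines, and at 120 sites the shortfall goes. Even the direction is not fixed. If patient effects persist fully between visits (assumed CV 0.5), the within-patient test has 76 to 88% against about 45% for a last-visit t-test. If they persist only partly, group-by-time in a patient-intercept GLMM has a false-positive rate of 6 to 17% at SD 0.3 and 13 to 34% at SD 0.5 (correlation 0.8 down to 0).
- A reader might infer that the protocol excludes baseline from the model. It does not: the terms are unstated, and a repeated-visit GLMM could include baseline as a visit or as a covariate.

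What the defence does not answer is that the protocol itself states outcome, power and model without tying them together, and that a nearly free covariate is already collected.

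**Conclusion.** The point holds as a cheap improvement of minor severity. The stated power is correct for the unadjusted last-visit comparison under pure Poisson counts (94.4%), and omitting baseline does not bias the comparison. Naming the sized contrast as the primary test and adjusting it for log baseline PI costs 0.1 points in the GLMM and about 0.6 in a last-visit fit on the protocol's inputs. If baseline does not predict follow-up, the cost is at most about 1 point in the GLMM and about 2 in single-visit linear models. The size of the gain is an assumption throughout: nothing at correlation 0, and 1.7 to 7.0 points at 0.5 with log SD 0.3 to 0.5.

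**What to change.** Add two statements to the Statistical Analysis Plan section and align the primary outcome wording with them.

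1. The primary test is the group contrast at the last visit (12 months). It comes from the Poisson GLMM fitted to the post-baseline visits, with log baseline PI as a covariate, group, visit, group-by-visit, the site offset and a patient random effect.
2. The power of at least 90% refers to the unadjusted last-visit comparison under pure Poisson counts.

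The price is one degree of freedom and the small power cost given above; no new data or patients are needed. Two limits should be accepted openly: the sizing still contains no baseline, and the adjusted contrast is a rate ratio, so the outcome's 10% of sites needs rewording or a supporting absolute difference. If the investigators want change tested as group-by-time instead, the trial should be re-sized for that test with a stated baseline PI and between-patient variance. Under the pure Poisson, 48-site illustration, 90% would need n = 10.508 × (1/12 + 1/8 + 2/(48b))/0.1644, which is about 24, 20, 19 and 18 per arm at mean baseline PI of 25%, 40%, 55% and 70%. The last two are not robust, since binomial counts already reach 90% there with 16.
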